#### **9.2.3 Matching**

For pregnant women with migraine, cohorts will be matched 1:4 on LMP date and gestational age. If there is sufficient sample size and overlap in the distribution of covariates to adjust for confounding, comparative analyses will be conducted, controlling for confounders using inverse probability of treatment weighted analyses.

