### **9.3 Variables**

#### **9.3.1 Exposure Assessment**

Pregnant women who have pharmacy claims for erenumab-aooe (identified using NDC codes) in the 112 days prior to the LMP date (to allow for the half-life of erenumab) or during the pregnancy will be considered exposed to erenumab-aooe.

Exposure to erenumab-aooe will be categorized by dose (70 mg versus 140 mg), by length of exposure, and by timing in relation to trimester of pregnancy: before the last menstrual period (LMP, in the 112 days prior to the EDC, this is the exposure window of interest for major malformations), during the first trimester (from the LMP to 90 days after the LMP), during the second trimester (from day 91 after the LMP to day 180 after the LMP), and during the third trimester (from day 181 after the LMP to the end of pregnancy) (see [Section 9.3.1.1](#) for definitions of LMP).

For the comparator cohorts, comparator group A will include pregnant women with migraine who do not have pharmacy claims for erenumab-aooe in the 112 days prior to the LMP but do have evidence of the use of other preventive migraine medications. Comparator group B will include pregnant women with migraine who do not have pharmacy claims for erenumab-aooe or other anti-CGRP medications 112 days prior to the LMP date or during pregnancy

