### 9.3.3 Covariate Assessment

Study cohorts will be described according to baseline covariates. Demographic attributes will be determined on the cohort entry date while others will be assessed during the baseline period, unless otherwise specified. All covariate information will be ascertained through inpatient and/or outpatient claims for diagnoses and procedures, and through pharmacy claims utilizing ICD-10 CM for diagnoses; ICD-10 PCS, CPT, or HCPCS codes for procedures; and GPI or NDC codes for dispensings. Additional details will be provided in the Statistical Analysis Plan (SAP) and the Medical Record Plan (MRP).

Covariates to be assessed include the following:

- Maternal age at estimated LMP (in years)

- Maternal race, if available

- Calendar year at estimated LMP

- Geographic region of health plan

- Migraine characteristics (eg, migraine with aura, chronic migraine)

- Comorbid conditions at baseline (eg, chronic hypertension, hyperlipidemia, diabetes, polycystic ovarian syndrome, hypothyroidism, hyperthyroidism, depression, anxiety, epilepsy), identified through ICD-10-CM diagnosis codes

- Medications in the baseline period (eg, acute and preventive migraine treatments, other treatments not for migraine, suspected teratogenic medications), identified through NDC codes or HCPCS codes

- Adverse events during pregnancy (eg, pre-eclampsia, gestational diabetes), identified through ICD-10-CM diagnosis codes

- Concomitant medications with claims after or a days supply that overlaps the LMP date and by trimester during the pregnancy (eg, acute migraine treatments, other treatments not for migraine, suspected teratogenic medications), identified through NDC codes or HCPCS codes

- History of obstetric outcomes (eg, prior pregnancies, multiple gestation, outcomes of prior pregnancies including spontaneous abortions) using all available history

- Use of prenatal testing

- Resource utilization (eg, number of prenatal visits, types of providers visited, emergency department visits)

- Body mass index, if available

- Alcohol, tobacco, and substance abuse, if available

Exposure to infections during pregnancy, if available  
 Previous history of congenital malformations, if available

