### 9.3.4 Validity and Reliability

#### *Identification of pregnancy and timing of exposure assessment during pregnancy*

Administrative databases can be useful in the assessment of prenatal drug exposure, and estimation of the LMP is necessary to classify exposure. Incorrect gestational age information can lead to misclassification of medication exposure during specific periods of pregnancy. Since there are no definitive diagnosis codes that clearly indicate the last menstrual period, pregnancy duration, or gestational age, diagnosis and other procedure codes have been recommended and utilized to determine the LMP. Approaches to arrive at the LMP in patients with live birth outcomes has been studied in administrative claims data using ICD-9 coding and have been shown to accurately identify most of these pregnancies (Ailes EC et al, 2016; Margulis AV et al, 2015; Naleway et al, 2013); however, there is no validated approach for pregnancies ending in non-live outcomes, and no studies have examined the impact of changes in ICD-10 coding

We previously tested the feasibility of three approaches (see Appendix B for details) in the MarketScan CCE databases to identify the LMP among pregnancies resulting in fetal death (Hornbrook et al, 2007; Kharbanda et al, 2012; Glaxo SmithKline 2017).

Results from the feasibility analysis estimating the mean and median gestational age (in weeks) using the three different methods are presented in Table 1. We propose to use an approach like the one described by Hornbrook et al, 2007 which uses outcome-specific estimates of gestational age developed by the Centers for Disease Control and Prevention. The percent agreement between the claims-based algorithm and medical record ranged from 87.5 to 96.3% for non-live birth outcomes (eg, therapeutic abortion, spontaneous abortion, and stillbirth), and from 86.6% to 100% for dates of these non-live birth outcomes.

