#### 9.6.2.4 Analysis of the Primary, Secondary, and Exploratory Endpoint(s)

##### 9.6.2.4.1 Analysis of the Primary Endpoint

Frequencies and the proportions (95% CIs) of major congenital malformations, in infants born to the following three cohorts of women with migraine, will be estimated: (1) those exposed to erenumab-aooe immediately prior to or during pregnancy, (2) those exposed to other preventive migraine medications immediately prior to or during pregnancy, and (3) those unexposed to any migraine preventive medications, including erenumab-aooe.

If there is sufficient sample size and adequate overlap in the distribution of confounding variables, formal comparisons to estimate odds ratios and corresponding 95% CIs will be undertaken. We will use inverse probability of treatment weights to address confounding. We will fit a logistic regression model for the conditional probability of treatment,  $Pr(A_i = a|L_i)$ , where  $L_i$  is a vector of measured baseline confounders of the exposure and the outcome. The conditional probability of treatment given a set of covariates is commonly referred to as the propensity score (PS), and a histogram of the overlap in the propensity score will be presented. IP of treatment weights will be constructed as:

$$\widehat{W}_i^2 = \frac{1}{\widehat{Pr}(A_i = a|L_i)}$$

For the analyses described here,  $L_i$  will be based on subject-matter knowledge (see covariates identified in [Section 9.3.3](#)).

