#### **9.8.1.3 Confounding**

Confounding by baseline covariates will be addressed with the use of inverse probability of treatment weights. We rely on subject matter knowledge to include candidate confounding variables in our analyses, but residual confounding may exist as a result of unmeasured or incomplete confounders (eg, obesity, use of alcohol, smoking, illicit drug use) or unknown confounders. We will include even weak confounders in the final analysis, sacrificing precision of our final effect estimates by guarding against the potential bias that might be introduced by omission of the confounder. The approach to address unmeasured confounders is addressed in [section 9.8.4](#).

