## Appendix B. Feasibility Assessment and Comparison of Methods for Timing of Exposure Assessment During Pregnancy

Administrative databases can be useful in the assessment of prenatal drug exposure, and estimation of the LMP date is necessary to classify exposure. Incorrect gestational age information can lead to misclassification of medication exposure during specific periods of pregnancy. Since there are no definitive diagnosis codes that clearly indicate the last menstrual period, pregnancy duration, or gestational age, diagnosis and other procedure codes have been recommended and utilized to determine the last menstrual period (LMP). Approaches to arrive at the LMP in patients with live birth outcomes have been thoroughly studied in administrative claims data and have been shown to accurately identify most of these pregnancies ([Ailes EC et al, 2016](#); [Margulis AV et al, 2015](#); [Naleway et al, 2013](#)); however, there is no validated approach for pregnancies ending in non-live outcomes.

We previously tested the feasibility of three approaches in the MarketScan CCE databases to identify the LMP among pregnancies resulting in fetal death ([Hornbrook et al, 2007](#); [Kharbanda et al, 2012](#); [Glaxo SmithKline 2017](#)). To test the first approach ([Hornbrook et al, 2007](#)), we assigned outcome-specific gestational age estimates based on national averages from the literature ([Martin et al, 2003](#); [Copper et al, 1994](#)). Assigning a fixed estimate (eg, patients with stillbirths were assigned a gestational period of 28 weeks) yielded no variability in the gestational age assignment among patients with identical outcomes, which did not accurately reflect the true date of the LMP. However, the approach provided solutions to address pregnancy durations that were incompatible with the respective pregnancy outcomes, overlapping pregnancy episodes, and subsequent pregnancy episodes, which are described in more detail in [Section 9.3.1.1](#)).

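### Section 9.2.3 matches on gestational age without a time point; on the only definition given this fixes the end of pregnancy and nearly fixes pregnancy loss, and the propensity-score covariate list contradicts its own baseline label.

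*Protocol*

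**What the plan says.** Protocol Section 9.2.3 states for the pregnant-women cohorts: "cohorts will be matched 1:4 on LMP date and gestational age". This matching is not conditional; only the weighted comparison that follows it depends on sample size and overlap.

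Section 9.3.1 defines exposure as a claim in the "112 days prior to the LMP date (to allow for the half-life of erenumab) or during the pregnancy".

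Section 9.3.1.1 takes gestational age from Z3A codes for the identified end of the pregnancy episode. Where those are missing it uses outcome-based lengths, refined by other week or trimester codes. Section 9.3.4 proposes an approach "which uses outcome-specific estimates of gestational age", and Table 1 reports gestational age by outcome (Method 1 means: 9.9 weeks for spontaneous abortion, 27.8 for stillbirth). Appendix B says that assigning a fixed estimate in this way "yielded no variability in the gestational age assignment among patients with identical outcomes".

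For the propensity score, Section 9.6.2.4.1 describes L_i as baseline confounders but says it "will be based on subject-matter knowledge (see covariates identified in" Section 9.3.3. That list includes "Adverse events during pregnancy (eg, pre-eclampsia, gestational diabetes), identified through ICD-10-CM diagnosis codes" and "Resource utilization (eg, number of prenatal visits, types of providers visited, emergency department visits", as well as concomitant medication by trimester and infections during pregnancy. Section 9.2.4 sets the baseline period as the 365 days before LMP. Section 9.8.1.3 adds: "We will include even weak confounders in the final analysis". Section 9.6.2.4.2 applies the same weights to the secondary outcomes.

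**The concern.** The exposure window opens 112 days before LMP, so the length of the pregnancy at its end follows exposure for every woman exposed before LMP, and follows the earliest erenumab-aooe dispensing for everyone else. It also all but determines the outcome: spontaneous abortion is a loss before 20 weeks and stillbirth a death at 20 weeks or later. A comparator chosen to share both LMP date and pregnancy length with a woman who miscarried at 9 weeks is a woman whose own pregnancy ended at 9 weeks, most probably also by miscarriage.

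At stake are two of the four safety outcomes, with false reassurance as the likely error. A larger sample would only make the wrong answer look more precise. Because the matching is unconditional, the comparators' descriptive loss proportions in the interim and final reports would be affected even if no formal comparison is ever run.

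The propensity-score wording is a second, separate problem. If the 9.3.3 list is used as it stands, the weights adjust for events after exposure, some of which depend on how long the pregnancy lasted.

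**Working it through.** **The plan's own figure.** The protocol gives no figure for the pregnancy-loss comparisons. Its nearest calculation is Table 2: 425 exposed live births for a relative risk of 2.00 in malformations. With p1 = 0.06, p0 = 0.03, 1:4 allocation, 80% power and two-sided alpha 0.05 (alpha is assumed from the 95% intervals), the pooled proportion is (0.06 + 4×0.03)/5 = 0.036, and

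n = [1.96·√(0.036×0.964×1.25) + 0.842·√(0.0564 + 0.0291/4)]² / 0.03² = 428.

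This agrees with 425. It does not bear on the bias below.

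**What the match fixes.** LMP date + gestational age at the outcome = end date of pregnancy. If nearly all pregnancies ending before 20 weeks are spontaneous abortions, comparators matched on that length have the same loss proportion as the exposed women. Take an assumed 15% unexposed risk and a true OR of 2.0:

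- exposed odds = 2 × 0.15/0.85 = 0.353, so exposed risk = 0.353/1.353 = 0.261;
- matched comparators' risk is also 0.261, so the matched OR is 1.0.

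The 1.0 comes from the 20-week cut and does not depend on the 15%.

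**Allowing for induced abortion.** Let a share q of each cohort end early by induced abortion, and treat all endings before 20 weeks as one stratum. The matched comparators' risk is (0.261 + q) × 0.15/(0.15 + q).

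- q = 0.02: 0.281 × 0.882 = 0.248; OR = 0.353/(0.248/0.752) = 1.07.
- q = 0.20: 0.461 × 0.429 = 0.198; OR = 0.353/(0.198/0.802) = 1.43.

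A simulation with weekly competing hazards and matching on the exact week of pregnancy end took a true OR of 2.2 to 1.08, 1.18, 1.30 and 1.51 at 2, 5, 10 and 20% induced abortion.

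**Simulation of the alternatives.** 2,000,000 pregnancies with exposure randomised, so there is no confounding. All rates are assumptions: spontaneous abortion 15% unexposed, at about 10 weeks; stillbirth 0.6% of the remaining unexposed pregnancies; live birth at about 39 weeks; no induced abortion.

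| Analysis | True OR 2.0 | True OR 1.5 |
|---|---|---|
| No post-exposure conditioning | 2.01 | 1.50 |
| Matched on gestational age at pregnancy end (exact week, or 4-, 8-, 13-week bands) | 1.00 | 1.00 |
| Matched on gestational age at exposure, women still pregnant | 2.00 | 1.50 |
| Weighted on prenatal visits, visit rate unaffected by exposure | 1.06 | 1.03 |
| Weighted on visits, exposed visit rate ×1.3 | 1.35–1.37 | 1.31–1.32 |
| Weighted on visits, exposed visit rate ×0.8 (with an unmeasured risk factor) | 0.90 | 0.87 |
| Weighted on pre-eclampsia and gestational diabetes only | 1.97 | 1.48 |
| Stillbirth, crude → matched on end gestational age | 1.75 → 1.13 | 1.39 → 1.07 |

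The first seven rows are spontaneous-abortion odds ratios. In the matched row for a true OR of 2.0, the comparators' spontaneous-abortion proportion moves from 15.0% to 26.2%. That is the distortion a purely descriptive table would show.

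**Is another gestational age available?** For a woman with claims only before LMP, gestational age at exposure does not exist. Comparator group B has no preventive-drug claim to date it from. The Study Design Schema and Section 9.2.4 mention an index date, but no exposure-day index is defined for any cohort. A programmer following the text has only gestational age at the outcome.

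**The case against.** The strongest reply is that Section 9.2.3 does not say gestational age at pregnancy end. The protocol also uses gestational age as the time scale for placing exposure, and draws on trimester-of-care codes. If gestational age at exposure among ongoing pregnancies was meant, there is no bias (2.00 recovered). It stands that the time point is unstated, so a reader should not infer a settled decision to match on the outcome. The benign reading is nevertheless written nowhere and cannot be applied to women exposed only before LMP.

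A reader might also infer that the propensity model is planned to include every 9.3.3 item and will therefore push results toward no effect. The documents do not support that. Sections 9.6.2.4.1 and 9.8.1.3 both say baseline, Section 9.8.1.3 calls the variables candidates, and the 9.3.3 list also serves a descriptive objective. This is a contradiction to resolve. If the list were followed, the bias has no fixed direction: weighting on visits gives 0.90 to 1.37 for a true 2.0, and complications alone barely matter for spontaneous abortion (1.97).

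Nor do all in-pregnancy items follow exposure. For a woman first exposed in the second trimester, first-trimester medication and infections come earlier and may be proper confounders. A strict cut at LMP would also leave suspected teratogen use during pregnancy unadjusted in the malformation comparison. Both points stand and shape the fix.

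The Appendix B remark on lack of variability concerns a feasibility test of fixed values; the current plan uses Z3A codes first. That weakens the remark as evidence, but Z3A codes taken at the end of the episode still measure pregnancy length at the outcome.

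Finally, the demonstrated effect concerns secondary outcomes whose formal comparison is conditional. That is correct. No effect on the primary outcome, and no quantified effect on small-for-gestational-age, has been shown.

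**Conclusion.** The matching rule needs correcting. On the only gestational age the protocol derives, it conditions on the end of pregnancy. It drives the spontaneous-abortion odds ratio toward 1 (true 2.0 to about 1.0 without induced abortion; true 2.2 to 1.08–1.51 with 2–20% induced abortion), attenuates stillbirth (1.75 to 1.13), and distorts the comparators' descriptive loss proportions. The figures rest on assumed loss rates, timing and induced-abortion shares, none of which the protocol gives. The near-complete loss of the spontaneous-abortion effect when few other pregnancies end early follows from the 20-week definition itself.

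The propensity-score part holds as an internal contradiction between the baseline wording (Sections 9.2.4, 9.6.2.4.1, 9.8.1.3) and the cited 9.3.3 list. If the list were followed, size and sign would be uncertain, with prenatal visits the item that matters most.

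**What to change.** In Section 9.2.3, match on LMP date only. For exposure that first occurs after LMP, match on gestational age at the earliest erenumab-aooe dispensing, choosing comparators still pregnant on that day. State that gestational age at pregnancy end is never a matching variable.

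In Section 9.6.2.4.1, limit L_i to 9.3.3 items measured before time zero, defined as LMP or, for women first exposed during pregnancy and their comparators, the match day. Report later items descriptively, and address suspected teratogen use after time zero in a sensitivity analysis.

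The cost is a rewording of two sections, slightly more matching code and one extra sensitivity analysis. No new data are needed.

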#### **9.2.4 Baseline Period**

The baseline period to assess relevant covariates, such as demographics, comorbidities, and concomitant medications, will be the 365 days prior to the LMP date. To evaluate history of obstetric outcomes (eg, prior pregnancies, multiple gestation, outcomes of prior pregnancies including spontaneous abortions), we will use all available data prior to the index date.

#### **9.2.5 Study Follow-up**

The study will start in May 2019 and end in November 2027. Because this study uses secondary data that has already been collected, data for analysis will be included starting from May 2018 when erenumab-aooe was approved in the US. Women will be followed for pregnancy outcomes (spontaneous abortion or stillbirth) from their LMP date through the end of their pregnancy date, and all live-born infants will be followed for outcomes from birth (eg, small-for-gestational age) through the end of their first year (eg, major congenital malformations). Women with migraine or their infants will be censored when their enrollment in the database ends.

### **9.3 Variables**

#### **9.3.1 Exposure Assessment**

Pregnant women who have pharmacy claims for erenumab-aooe (identified using NDC codes) in the 112 days prior to the LMP date (to allow for the half-life of erenumab) or during the pregnancy will be considered exposed to erenumab-aooe.

Exposure to erenumab-aooe will be categorized by dose (70 mg versus 140 mg), by length of exposure, and by timing in relation to trimester of pregnancy: before the last menstrual period (LMP, in the 112 days prior to the EDC, this is the exposure window of interest for major malformations), during the first trimester (from the LMP to 90 days after the LMP), during the second trimester (from day 91 after the LMP to day 180 after the LMP), and during the third trimester (from day 181 after the LMP to the end of pregnancy) (see [Section 9.3.1.1](#) for definitions of LMP).

For the comparator cohorts, comparator group A will include pregnant women with migraine who do not have pharmacy claims for erenumab-aooe in the 112 days prior to the LMP but do have evidence of the use of other preventive migraine medications. Comparator group B will include pregnant women with migraine who do not have pharmacy claims for erenumab-aooe or other anti-CGRP medications 112 days prior to the LMP date or during pregnancy

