**Exposure period and definition:**

*Erenumab-aooe exposed:* claims for erenumab-aooe in the 112 days prior to the index date or during the pregnancy period  
*Comparator Cohort:* no claims for erenumab-aooe in the 112 days prior to the LMP or during the pregnancy period

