## **8. Research Question and Objectives**

### **8.1 Primary**

The primary objective is to estimate and compare the proportion of live-born infants with major congenital malformations among (1) women with migraine directly exposed to erenumab-aooe prior to and during pregnancy, (2) women with migraine exposed to other preventive migraine medications prior to or during pregnancy (comparator group A), and (3) women with migraine not exposed to erenumab-aooe or other preventive migraine medications prior to or during pregnancy (comparator group B). Comparative analyses will be undertaken if there is sufficient sample size and adequate distribution of covariates to adjust for confounding.

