#### **9.2.2.2 Exclusion Criteria**

Women who are exposed to known teratogens (eg, valproate or topiramate) or other CGRP antagonists will be excluded if exposure to these substances occurs within five of their half-lives prior to LMP.

For comparator cohort B, women who have pharmacy claims for any preventive migraine medications will be excluded.

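### Section 9.3.1 does not bar erenumab use during pregnancy from comparator A, so the same pregnancy can meet both the exposed and the comparator A definitions

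*Protocol*

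**What the plan says.** **Exposed cohort.** Protocol Section 9.3.1 starts from "Pregnant women who have pharmacy claims for erenumab-aooe (identified using NDC codes) in the 112 days prior to the LMP date" and adds a second route into the cohort: "or during the pregnancy will be considered exposed to erenumab-aooe". Either window is enough.

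**Comparator A.** The same section describes women "who do not have pharmacy claims for erenumab-aooe in the 112 days prior to the LMP but do have evidence of the use" of other preventives. Only the window before the LMP is named.

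**Comparator B.** The next sentence of 9.3.1 describes women "who do not have pharmacy claims for erenumab-aooe or other anti-CGRP medications 112 days prior to the LMP date or during pregnancy". Here pregnancy is covered, but the only drugs barred are erenumab and other anti-CGRP products.

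**Elsewhere in the protocol.**
- The Study Design Schema, under exposure period and definition, requires of the comparator cohort "no claims for erenumab-aooe in the 112 days prior to the LMP or during the pregnancy period".
- Section 8.1 describes B as "women with migraine not exposed to erenumab-aooe or other preventive migraine medications prior to or during pregnancy (comparator group B").
- Section 9.2.2.2 states: "For comparator cohort B, women who have pharmacy claims for any preventive migraine medications will be excluded". It gives no time window.
- Section 9.6.2.4.1 describes the third cohort as unexposed to every migraine preventive, erenumab included.
- Sections 9.6.2.4.2 and 9.6.2.5.1 set the exposed women against women with no erenumab either before or during pregnancy.

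**The concern.** Section 9.3.1 is where a programmer will look for the cohort rules, and its rule for A is narrower than its rule for exposure. The overlap consists of women on another preventive, with no erenumab claim in the 112 days before the LMP, who first fill erenumab once pregnant.

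Two things would follow if the sentence were applied literally. First, the inverse probability weights in Section 9.6.2.4.1 model the probability of the treatment received and so need one treatment value per pregnancy; a pregnancy that qualifies for two cohorts has none. Section 9.2.3 also matches on LMP date and gestational age, and a pregnancy counted in both cohorts would match itself exactly. Second, erenumab-exposed pregnancies inside A move A's outcome proportion toward that of the exposed cohort. If erenumab raises risk, the erenumab-versus-A estimate is biased toward no effect, which in a post-marketing safety study is false reassurance.

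**Working it through.** **Step 1. Pairwise check of the definitions.**

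| Pair | Section 9.3.1 read alone | Whole protocol |
|---|---|---|
| Exposed and A | Overlap: first erenumab fill in pregnancy plus another preventive | Conflict. The schema bars it, and 9.6.2.4.2 and 9.6.2.5.1 imply that it is barred; the 9.3.1 sentence admits it |
| A and B | Overlap: users of preventives that are not anti-CGRP | No overlap: 9.2.2.2 excludes them from B, and 8.1 and 9.6.2.4.1 agree |
| Exposed and B | No overlap: B bars erenumab before the LMP and during pregnancy | No overlap |

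One pair is left in real conflict, exposed and A. The definitions of A in Sections 8.1, 9.2.2.1 and 9.6.2.4.1 do not settle it, because they describe A by use of other preventives and do not mention erenumab. The exclusion in 9.2.2.2 covers other CGRP antagonists and known teratogens, and only before the LMP.

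**Step 2. The plan's own figure, for context.** Table 2 gives 425 live births in the exposed group for a relative risk of 2.00. Section 9.5 supplies 3% background prevalence, 1:4 matching and 80% power. A two-sided alpha of 0.05 is my assumption, since the protocol states none. With p1 = 0.06, p0 = 0.03, k = 4 and pooled proportion (0.06 + 4 × 0.03)/5 = 0.036:

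n = [1.960 × √(0.036 × 0.964 × 1.25) + 0.842 × √(0.06 × 0.94 + 0.03 × 0.97/4)]² / 0.03²

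n = (0.408 + 0.212)² / 0.0009, which gives 428 when unrounded terms are carried.

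This agrees with 425 to within 1%. Power at 425 is 79.8%, so this row has no reserve.

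**Step 3. What contamination of A could do.** Let c be the share of A with erenumab in pregnancy. The documents give no value for c, so every entry below is an assumption. If those women carry the full exposed risk, A's risk becomes 0.03(1 − c) + 0.06c, and

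observed RR = 0.06 / [0.03(1 − c) + 0.06c] = 2/(1 + c).

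| Assumed c | Risk in A | Observed RR | Power at 425 exposed |
|---|---|---|---|
| 0% | 3.00% | 2.00 | 79.8% |
| 1% | 3.03% | 1.98 | 78.9% |
| 2% | 3.06% | 1.96 | 78.0% |
| 5% | 3.15% | 1.90 | 75.3% |
| 10% | 3.30% | 1.82 | 70.3% |
| 20% | 3.60% | 1.67 | 59.5% |

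For malformations this is the most dilution a given c could cause, as long as contaminating women carry no more than the exposed-cohort risk. Women who start erenumab late in pregnancy would not plausibly carry the full doubled malformation risk, so the actual shift at that c would be smaller.

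**The case against.** The strongest reply is that the intent is clear and one phrase has been dropped. Section 9.3.1 itself says that a claim in pregnancy makes a woman exposed, the schema bars such claims from the comparator cohort, and Section 9.6.2.5.1 lists users of other preventives as a subgroup of women unexposed to erenumab before or during pregnancy. The weighting model also presumes one treatment per pregnancy. This stands as evidence of what was meant, and it supports the fix. It does not remove the conflict. The B sentence beside it does cover pregnancy, and 9.3.1 calls the period before the LMP the window of interest for malformations, so the narrower rule for A could be taken as deliberate.

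The reply is also right about magnitude. No source supports any value of c, and the wording for A already excludes erenumab in the 112 days before the LMP. For the primary outcome, mainly women who start early in pregnancy would matter.

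A reader might go further and infer that all three cohorts overlap, or that the untreated-migraine reference is lost because users of beta-blockers or tricyclics can enter B. The documents do not support either. Exposed and B never overlap, even in 9.3.1 read alone, and A and B overlap only if the explicit exclusion in 9.2.2.2 is ignored. Sections 8.1 and 9.6.2.4.1 agree with that exclusion.

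**Conclusion.** The concern holds for comparator A. Section 9.3.1 contradicts the Study Design Schema, the unexposed contrast in 9.6.2.4.2 and 9.6.2.5.1, and its own definition of exposure. If followed literally, it puts exposed pregnancies into a comparator of the primary objective, with bias toward no effect. That conclusion rests on the text alone and needs no assumed figure.

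The size of the bias cannot be obtained from the documents. The figures in Step 3 depend on an assumed share, a true relative risk of 2.0 and full exposed risk in every contaminating pregnancy. They illustrate a limit and are not an estimate.

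For comparator B the finding is only a wording mismatch. Section 9.3.1 is looser than 8.1, 9.2.2.2 and 9.6.2.4.1, and the time window is inconsistent: 8.1 refers to the period before or during pregnancy, 9.2.2.2 gives no window, and 9.3.1 uses 112 days before the LMP or during pregnancy.

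**What to change.** In Section 9.3.1:

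1. Define comparator A as women with no erenumab claim in the 112 days before the LMP or during pregnancy, and with another migraine preventive in its exposure window.
2. State that any woman with a qualifying erenumab claim is assigned to the exposed cohort only, whatever other preventives she uses.
3. Align comparator B with Sections 8.1 and 9.2.2.2, so that it requires no claim for any migraine preventive. Give one time window for that exclusion and use it in 8.1, 9.2.2.2 and 9.3.1.

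The cost is a few lines of protocol text, one additional cohort-selection condition and a slightly smaller comparator A pool. The Table 2 requirement does not change, because it already assumes a comparator group at background risk.
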